4.1.1. Mechanisms of Action

MDMA interacts with plasma monoamine transporters and storage vesicles to increase extracellular levels of 5-HT, dopamine, and norepinephrine (Cozzi et al. 1999; Fitzgerald and Reid 1990; Gudelsky and Nash 1996; Hiramatsu and Cho 1990; Kankaanpaa et al. 1998; Nash and Brodkin 1991; Rudnick and Wall 1992; Schuldiner et al. 1993). Direct MDMA stimulation of postsynaptic 5-HT_{2A} receptors and α-2 adrenoceptors also contributes to MDMA's effects. For example, dopamine release is also indirectly increased by MDMA stimulation of 5-HT_{2A} receptors on GABAergic striatonigral neurons (Gudelsky and Nash 1996; Koch and Galloway 1997; Palfreyman et al. 1993; Schmidt et al. 1992; Yamamoto et al. 1995).

Although the specific mechanisms of MDMA's therapeutic effects are not fully understood, several observations and hypotheses can be made. Increased extracellular levels of dopamine and norepinephrine are known to be important to the reinforcing effects of psychostimulants (Ritz and Kuhar 1993; Rothman et al. 2001; Wise and Bozarth 1985). These neurotransmitters likely play a similar role with MDMA, producing feelings of excitement, euphoria, and well-being. When the D₂ receptor antagonist haloperidol was combined with MDMA, human volunteers reported less positive

mood and greater anxiety (Liechti and Vollenweider 2000a), findings in keeping with these hypotheses. Central dopamine and norepinephrine are also thought to regulate readiness for action and arousal, with dopamine possibly mediating behavioral readiness, and locus coeruleus norepinephrine mediating conscious registration of external stimuli (Clark et al. 1987; Robbins and Everitt 2000). Increasing these neurotransmitters may therefore place the individual in a state of alertness that is ideal for recalling or even re-experiencing state-dependent memories of stressful events. This potentially aversive state may be modified by MDMA effects on both the serotonergic system and postsynaptic α -2 adrenoceptors.

MDMA effects on the serotonergic system are likely important for its therapeutic effects. MDMA induces 5-HT release and is a 5-HT₂ agonist. Serotonergic dysfunction is associated with anxiety, aggression, and depression. Increasing 5-HT release is thought to have opposite effects. For example, stimulation of 5-HT_{1A} and 5-HT_{1B} receptors decreases anxiety and aggression in rodent behavioral studies (Brunner and Hen 1997; Graeff et al. 1996) and likely contributes to reduced defensiveness and increased self-confidence reported after MDMA. 5-HT_{1A} receptors in the hippocampus have also been specifically hypothesized to enable disengaging from previously learned associations if they lead to adverse outcomes (Guimaraes et al. 1993). MDMA also has moderate 5-HT_{2A} activity (Nash et al. 1994), which leads to modest alterations in perception of meaning (Liechti et al. 2000b), possibly facilitating new ways of thinking. Case reports suggest increasing extracellular 5-HT levels may facilitate recovery of remote memories (Robertson 1997), a phenomenon that has been reported by psychotherapists administering MDMA to patients (Downing 1985). Studies in humans suggest that serotonergic activity plays an important role in generating the subjective effects of MDMA, since co-administration of a serotonin uptake inhibitor reduces most subjective effects (Liechti et al. 2000A; Tancer and Johanson 2004). Thus, MDMA effects on the serotonergic system may decrease anxiety and aggression and create a state of mind that is conducive to psychotherapy.

Direct MDMA stimulation of postsynaptic α -2 adrenoceptors may modify this state by altering the balance of α -1 and α -2 stimulation, allowing the individual to remain emotionally calm despite noradrenergic activation. MDMA is an α -2 agonist (Lavelle et al. 1999). Like other α -2 agonists, such as guanfacine and clonidine (Arnsten 1998), MDMA produces feelings of calmness and relaxation (Cami et al. 2000). It is worth noting that open label trials suggest that clonidine may be helpful for treating symptoms of PTSD (Harmon and Riggs 1996; Kinzie and Leung 1989), indicating that α -adrenergic action may possess anxiolytic effects in humans.

4.1.2 Drug Activity Related to Proposed Action

MDMA has a unique profile of psychopharmacological effects making it well suited to intensive psychotherapy. In the context of psychotherapy, MDMA has been noted to reduce defenses and fear of emotional injury while enhancing communication and capacity for introspection (Greer and Tolbert 1998; Grinspoon and Bakalar 1986). Placebo-controlled clinical trials have confirmed that MDMA produces an easily-controlled intoxication characterized by euphoria, increased well being, sociability, self-confidence, and extroversion (Cami et al. 2000; Harris et al. 2002; Hernandez-Lopez et al. 2002; Liechti et al. 2000a; Liechti et al. 2001a; Liechti et al. 2000b; Liechti and Vollenweider 2000a; Tancer and Johanson 2001; Tancer and Johanson 2003; Vollenweider et al. 1998). These effects make it likely that MDMA would be useful in psychotherapeutic treatment of many different complaints.

The subject population of chronic PTSD patients was selected because of patient testimonials concerning the effectiveness of MDMA-assisted therapy and because the effects of MDMA have the potential to be particularly useful in the treatment of this disorder. PTSD is a condition that involves prominent fear responses. Revisiting traumatic experiences in psychotherapy is recognized to be of therapeutic value, and early clinical experience with MDMA is consistent with the hypothesis that it can increase therapeutic effectiveness in this population. Downing (1985) testified that MDMA was very helpful in treating a woman who experienced incapacitating panic attacks after sexual assault.

Anecdotal reports have been published of improvement in PTSD among people who took MDMA in therapeutic or quasi-therapeutic settings (Adamson 1985). These reports are consistent with the observations of other therapists that MDMA-assisted psychotherapy is particularly useful in patients with a history of child abuse or sexual assault (Greer 1985). Preliminary results were encouraging in a pilot study of MDMA treatment for 20 soldiers with combat-related PTSD, but political instability in Nicaragua prevented further research (Saunders 1993). In 2000, an MDMA/PTSD therapy study was approved in Spain (AEM #99-309), but has unfortunately been halted due to political concerns expressed by the local anti-drug authority (Bouso, 2003, communication to [name] and [name], January 15, 2003).

4.2. Secondary Pharmacodynamics

The psychotherapeutic effects of MDMA are accompanied by dose-dependent physiological effects including vasoconstriction and increased heart rate and blood pressure (Lester et al. 2000; Liechti et al. 2001; Mas et al. 1999; Tancer and Johanson 2001, Tancer and Johanson 2003 and see pp 44-48 of IND #63,384). Physiological effects of MDMA reach their maximum within 1 and 2 hrs after oral MDMA administration and have largely subsided within 6 hrs of drug administration (Gamma et al. 2000; Lester et al. 2000; Mas et al. 1999; Tancer and Johanson 2003; Vollenweider et al. 1998, see also Baggott et al. 2001). Data on maximum changes in heart rate and blood pressure collected from human studies published or in preparation in mid-2001 are summarized in Table 3.1 in the Investigators' Brochure. Data from more recent reports (e.g. Farre et al. 2004; Hernandez-Lopez et al. 2002; Lamers et al. 2003; Tancer and Johanson 2003) are similar to data from previous reports. Pre-treatment with a serotonin uptake inhibitor attenuated or prevented elevations in blood pressure and heart rate (Liechti and Vollenweider 2000), and the 5HT_{2A} receptor antagonist ketanserin reduced elevated diastolic pressure (Liechti et al. 2000a), while the D₂ antagonist haloperidol failed to attenuate any of the cardiovascular effects of MDMA (Liechti et al. 2000b). These findings suggest that cardiovascular effects are at least partially due to serotonergic activity. When given in controlled settings, MDMA produced only slight increases in body temperature (Harris et al. 2002; Lester et al. 2000; Liechti et al. 2000b; Tancer and Johanson 2003), with the increase undetected in a number of studies (de la Torre et al. 2000; Farre et al. 2004; Johanson et al. 2005; Liechti et al. 2000a).

On the basis of data from human studies of physiological effects, an initial dose of 25 mg is expected to have a minimal impact on blood pressure, heart rate, or body temperature, and effects are also expected to be minimal after a total dose of 37.5 mg MDMA, though findings from at least one study suggest that this dose might produce detectable increases in tension and relaxation (Harris et al. 2002). The initial dose of 125mg and the supplemental dose of 62.5 mg are identical to the doses used in the FDA and IRB-approved MAPS-sponsored study of MDMA-assisted therapy in people with anxiety associated with advanced-stage cancer (IND 63,384). The full dose of 125 mg, followed by a supplemental dose of 62.5 mg after 2.5 h are expected to produce significant increases in blood pressure and heart rate, but are not expected to produce sustained increases in heart rate or blood pressure above 170/100 mm Hg. It is expected that elevation in blood pressure and heart rate may be greater than after 125 mg, but with the increase in blood pressure and heart rate not greatly exceeding the elevation reported after 2.5 mg/kg MDMA. The physiological effects of a second dose of MDMA that is half the original dose and given two and a half hours after the first dose are not yet known. Administering a second dose of 100 mg MDMA a day after an initial 100 mg dose increased systolic blood pressure, diastolic blood pressure and heart rate to levels greater than seen after the initial dose, but not significantly greater. Likewise, an initial dose of 150 mg with a supplemental dose of 75 mg are likely to elevate blood pressure and heart rate to a greater degree than 125 mg and closer to those seen after 2 or 2.5 mg/kg.

MDMA dose-dependently and acutely increases cortisol, prolactin, and adrenocortictropic hormone concentrations (Farre et al. 2004; Grob et al. 1996; Grob et al. Unpublished; Harris et al. 2002; Mas et al. 1999; Pacifici et al. 2004; Tancer and Johanson 2003), while growth hormone is unchanged by up

to 125 mg MDMA (Mas et al. 1999). Increases in cortisol and prolactin peak at about 2 hours after MDMA administration. A second dose of 100 mg MDMA given four hours after an initial dose of 100 mg produced a second increase in cortisol during an interval when cortisol levels were declining (Pacifici et al. 2001), and a dose of 100 mg MDMA given 24 hours after an initial dose stimulated a greater release of cortisol, but not prolactin (Farre et al. 2004). In a study of the effects of 0.5 and 1.5 mg/kg MDMA in eight people, there was a trend for increased levels of the hormone dehydroepiandrosterone (DHEA) after 0.5 mg/kg MDMA, and a significant increase after 1.5 mg/kg MDMA (Harris et al. 2002), with DHEA levels peaking 2 to 3 h post-drug. Harris and colleagues failed to detect any changes in luteinizing hormone (LH), estradiol, progesterone or follicle stimulating hormone (FSH) in women participants. 40 mg MDMA acutely increased circulating levels of antidiuretic hormone (arginine vasopressin) in eight male volunteers (Forsling et al. 2001; Henry et al. 1998). Antidiuretic hormone reached maximum levels between 1 to 2 hours after MDMA administration. Increased retention of fluid is unlikely to be of any consequences in a clinical setting. Nonetheless, precautions will be taken to avoid dilutional hyponatremia, including providing electrolyte-containing beverages and restrictions on fluid consumption.

Studies conducted in Spain suggest that MDMA acutely affects the immune system (Pacifici et al. 1999;; Pacifici et al. 2000; Pacifici et al. 2001; Pacifici et al. 2002; Pacifici et al. 2004). These acute changes in immunologic function include reduced CD4 T-cell count, increased NK cell count, and decreased phytohaemoagglutin A-induced lymphocyte proliferation. MDMA decreased levels of the immune system stimulating and proinflammatory cytokine interleukin 2 (IL-2) and increased levels of the immunosuppressive and anti-inflammatory cytokine interleukin 10 (IL-10) (Pacifici et al. 2004; Pacifici et al. 2001). Generally, MDMA appears to decrease the concentration of Th1 cytokines and increase Th2 cytokines measured in blood. Immunological changes seen after an initial dose of MDMA are enhanced by a second dose of identical size given four hours after the first dose (Pacifici et al. 2001; Pacifici et al. 2002), and a second dose of identical size given 24 hours after the first dose produced the same immunological effects over the same time course, but with greater intensity than after the first dose (Pacifici et al. 2002). Given this data, it is possible that administering a smaller supplemental dose 2.5 h after the first dose will slightly enhance the immunological effects set in motion by the first dose. These acute changes are unlikely to be of consequence in healthy individuals and are of a similar magnitude to changes produced by other pharmacological agents. For example, the CD4 T-cell count decrease was similar in magnitude to that produced by 0.8 g/kg oral ethanol (the equivalent of 4-5 drinks) in the same report (Pacifici et al. 2001). The mechanism of immunomodulation is unclear but may be at least partly due to increased glucocorticoid levels or sympathomimetic activity, and activity at alpha adrenergic receptors (Connor et al. 2004). Serotonin release probably plays a role in these changes, since paroxetine pretreatment attenuated and in some cases eliminated immunological effects of MDMA (Pacifici et al. 2004) while only partially reducing elevated cortisol. Acute alterations in immune functioning after MDMA administration have also been noted in mice (House et al. 1995) and rats (Connor et al. 2000a; Connor et al. 2000b; Connor et al. 2004). This immunomodulation is an acute effect of MDMA and is not likely to persist for more than 48 hours after MDMA administration.

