2.6. Questions and Hypotheses

The following main questions are to be explored in the proposed study:

1. Can MDMA, in the doses to be used in this study, be safely administered in the population of treatment-resistant PTSD patients without any serious adverse events?
2. Will patients receiving the larger, fully active dose of MDMA, in combination with non-drug assisted psychotherapy, demonstrate greater symptomatic improvement than patients given an active placebo dose of MDMA in combination with non-drug psychotherapy?
3. Will patients receiving three MDMA sessions in combination with non-drug psychotherapy demonstrate an additional improvement compared to patients receiving only two sessions?
4. Can treatment effects of MDMA-assisted psychotherapy be maintained beyond end of treatment?

Based on the reviewed research, the following hypotheses were formulated:

Re 1. PTSD patients receiving the fully active dose of MDMA will not experience any serious adverse events. The supplemental dose of MDMA will be tolerated both in the low and fully active dose conditions.

Re 2. There will be trends for people receiving the fully-active dose of MDMA to demonstrate greater symptomatic improvement after receiving MDMA-assisted therapy than people receiving the low dose of MDMA, including greater reduction in symptom severity and intensity, and overall improvement in PTSD symptoms, as measured via the CAPS and PDS, with CAPS score serving as the primary outcome measure.

Re 3. 3 experimental MDMA-assisted sessions will lead to better results compared to only 2 experimental MDMA-assisted sessions, as measured via the CAPS and PDS, with CAPS score serving as the primary outcome measure.

Re 4. The treatment gains will remain stable at the 2, 6 and 12 months assessments.

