With participants carefully monitored for any indicators of adverse events, the initial doses of either 125 mg or 150 mg, and the cumulative dose of 187.5 mg or 225 mg respectively will prove to be tolerable and pose no more than minimal risk. The side effect profile is expected to increase with the higher dose but it is considered unlikely that there will be any Serious Adverse Events (SAEs) or any persisting side effects.

Table 1. Dose Regimen

	Initial Dose	Supplemental Dose	Cumulative Dose
Low Dose	25 mg	12.5 mg	37.5 mg
Fully Active Dose	125 mg	62.5 mg	187.5 mg
20% Larger Active Dose	150 mg	75 mg	225 mg

Supplemental doses for both the Low and the Fully Active dose conditions were chosen to be half the size of initial doses, and the dosage and schedule of dosing was chosen on the basis of case reports describing the use of MDMA in psychotherapy (Greer and Tolbert 1998; Stolaroff 2004, Styk 2007). Supplemental dosing performed 2.5 hours after the initial dose is expected to extend the course of drug effects without increasing their intensity. Both the Low and Fully Active dose conditions use supplemental doses that are half of the initial dose, to make dosing schedule equivalent across the conditions.

Participants will receive an initial dose of MDMA approximately 1 to 1.5 hours after they arrive at [name] office for each experimental session. If the investigators believe the participant is able to tolerate a supplemental dose and the participant agrees to take it, then a supplemental dose will be offered 2.5 hours later. The investigators will not administer the supplemental dose if the participant is exhibiting signs or symptoms that would place him or her at greater risk of experiencing a serious adverse event.

Each dose will consist of the specified amount of racemic MDMA mixed with an inactive substance, such as lactose, to prevent the investigators from distinguishing doses through weight or appearance of the capsules. Initial doses will be distinguished from supplemental doses through labeling them "Dose 1" and "Dose 2" or "first" and "second" dose to ensure that the correct dose is administered at the scheduled time. Each dose of MDMA will be administered along with 250 to 300 mL electrolyte-containing fluid. MDMA will be administered during each of the three experimental sessions, with the second and third session scheduled to fall two to four weeks after the previous experimental session.

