6.5.1 Main Analysis

Physiological Measures and SUD

Analysis #1

Goal: to test the presence of a main effect of condition (125 mg MDMA, 25 mg MDMA, 150 mg MDMA in Extended Assessment 2) on changes in vital signs and psychological distress,

Population: All enrolled, intention to treat, per protocol, partial crossover, Extended Assessment 2

Data included: Pre-drug average, maximum change (peak) and post-drug average SBP, DBP, HR, BT and SUD, number of participants with vital signs above clinical cut off and duration above clinical cut-off

Format of Analyses: One-way ANOVA per each experimental session, including sessions during Stage 1, Stage 2 and Stage 3

Between-Group Factor: Condition (125 mg MDMA, 25 mg MDMA, 150 mg MDMA in Extended Assessment 2)

Analysis #2

Goal: To test effects of condition, presence or absence of supplemental dose and time of session on physiological data and psychological distress during experimental sessions

Population: All enrolled, intention to treat, per protocol

Data included: Pre-drug average, maximum change (peak) and post-drug average SBP, DBP, HR, BT and SUD, number of participants with vital signs above clinical cut off.

Format of analysis: Repeated measures ANOVA

Time: Session (Experimental 1, Experimental 2, Experimental 3)

Between Groups Factors: Condition (125 mg MDMA, 25 mg MDMA) as between-group factor, and supplemental dose (given, not given) as second between-group factor.

Analysis #3

Goal: To test effects of condition, presence or absence of supplemental dose and time of session on physiological data and psychological distress during Stage 2 or Stage 3 sessions.

Population: Partial crossover, Extended Assessment 2

Data included: Pre-drug average, maximum change and post-drug average SBP, DBP, HR, BT and SUD, number of participants with vital signs above clinical cut off, and duration above clinical cut-off.

Format of analysis: Repeated measures ANOVA

Time: Crossover Session (Stage 2 Experimental Session 1, 2, and 3, Stage 3 Experimental sessions 1 and 2)

Between-Subjects factors: Supplement (present, absent)

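### SAP 6.5.1 tests the supplemental dose on summaries never confined to the time after it, so a blood-pressure or pulse effect can be diluted and the given-versus-not-given contrast biased

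*Protocol*

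**What the plan says.** Three places in the protocol raise the question. Section 4.2 states that the physiological effects of a second dose that is "half the original dose and given two and a half hours after the first dose are not yet known"; it also allows that elevations may exceed those after 125 mg. Section 2.8.1 says that supplemental dosing "is expected to extend the course of drug effects without increasing their intensity". Section 2.6 hypothesises: "The supplemental dose of MDMA will be tolerated both in the low and fully active dose conditions".

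SAP 6.5.1 Analysis #2 (Stage 1) has this goal: "To test effects of condition, presence or absence of supplemental dose and time of session on physiological data and psychological distress during experimental sessions". Its outcomes are "Pre-drug average, maximum change (peak) and post-drug average SBP, DBP, HR, BT and SUD, number of participants with vital signs above clinical cut off". The repeated factor is session number (1, 2, 3), and supplement given or not given is a between-group factor. Analysis #3 uses the same summaries for Stages 2 and 3 and adds duration above cut-off. The SAP does not say which readings form the post-drug average.

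On timing, Protocol 4.2 says that physiological effects "reach their maximum within 1 and 2 hrs after oral MDMA administration" and have largely gone by 6 h. The supplement is offered about 2.5 h after the first dose (2.8.5.1). Under 2.8.1 it is withheld from participants whose signs or symptoms suggest a raised risk.

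**The concern.** A reading taken before the supplement cannot be an effect of it. Analyses #2 and #3 ask what the supplement does, yet no outcome is restricted to readings after it, and the time factor does not look inside a session.

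Two things follow. A real rise after the supplement can be averaged down, or can sit below an earlier first-dose maximum and leave the peak unchanged. And since the decision to withhold depends on how the participant looks before the supplement, the earlier readings can differ between the given and not-given groups for reasons that the supplement did not cause. A finding of no supplement effect on vital signs would then be weak evidence on a safety question that the protocol itself leaves open, although Table 3 schedules the readings needed to address it.

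**Working it through.** The documents give no effect size or power for this analysis, so there is no plan figure to reproduce.

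**Inputs**
- Protocol Table 3: first dose at 10:00. Blood pressure and pulse at 10:30, 11:00, 11:30, 12:00, 12:30, 13:00, 13:30, 14:00, then hourly.
- Protocol 2.8.5.1: session of 6 to 8 h; supplement at about 2.5 h, so about 12:30. Exact reading times are at the therapists' discretion.
- Protocol 2.8.5: onset of effects 30 to 60 minutes after ingestion.
- Protocol Table 4, 125 mg: absorption constant 2.1253 per h, elimination constant 0.0923 per h.
- Assumption: the post-drug average is the plain mean of all readings after the first dose.

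**1. Post-drug average**

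Share of a post-supplement mean effect that is kept = readings after 12:30 / all readings after the first dose.

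| Measure | Before or at 12:30 | After, 6 h session | After, 8 h session | Share kept |
|---|---|---|---|---|
| BP, pulse | 5 | 5 | 7 | 5/10 = 0.50 to 7/12 = 0.58 |
| Temperature (every 60–90 min after 14:00) | 2 | 3 to 4 | 4 to 6 | 3/5 = 0.60 to 6/8 = 0.75 |
| SUDS (every 60–90 min after 14:00) | 2 | 2 to 3 | 3 to 5 | 2/4 = 0.50 to 5/7 = 0.71 |

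Sensitivity for BP and pulse: if the 13:00 reading comes too soon to show any effect, 4/10 = 0.40 to 6/12 = 0.50. If the average is weighted by time, 3.5/6 = 0.58 to 5.5/8 = 0.69. The pre-drug average keeps 0.

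**2. Bias from withholding**

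The earlier readings carry the remaining weight. Suppose that participants denied the supplement ran higher by h before 12:30, and that the supplement did nothing. The all-post-drug BP average would still be higher without the supplement by 5/12 h to 5/10 h (0.42h to 0.50h). That difference would offset a true rise.

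**3. Session peak**

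Assume a straight-line rise to a first-dose peak of 1, a straight-line fall, and a supplement response half as large, starting 2.5 h later. Example: peak at 1.5 h, 10% left at 6 h.
- First-dose response at 4.0 h: 1 − 0.9 × 2.5/4.5 = 0.50. The supplement adds its maximum of 0.50. Total 1.00, so the session maximum does not change.
- Highest reading after 12:30 without the supplement (13:00): 1 − 0.9 × 1.5/4.5 = 0.70. With the supplement it is 1.00, a rise of 0.30.

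Over peak times of 1, 1.5 and 2 h with 0, 10 or 20% left at 6 h, the session maximum is 1.00 to 1.10 times its value without the supplement, and unchanged in six of the nine settings. The largest case is peak 1 h with 20% left: at 3.5 h, 1 − 0.8 × 2.5/5 = 0.60, plus 0.50, gives 1.10. The session peak keeps 0 to 20% of the supplement's largest effect at a scheduled reading.

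**4. The contrary pattern**

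Adding two one-compartment curves, with concentration proportional to exp(−0.0923t) − exp(−2.1253t):
- First dose alone: maximum 0.830 at 1.54 h.
- With a half dose at 2.5 h, at 3.58 h: 0.718 + 0.5 × 0.804 = 1.120.
- Ratio: 1.120/0.830 = 1.35.

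In this case the session peak does rise. The maximum over scheduled readings keeps about 70% of the supplement's largest effect. This is a plasma calculation under linear kinetics, and Protocol 4.5 describes the kinetics as dose-dependent, so it serves only as an illustration.

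**The case against.** The strongest defence is that the peak and the average work as a pair. A flat peak with a higher average suggests a longer response; a clearly higher peak suggests a stronger one. The calculations bear this out in part: the maximum is 1.00 to 1.10 under the section 4.2 time course and 1.35 under the Table 4 kinetics. Moreover, if the supplement does not raise the session maximum, an unchanged peak is the right answer to the expectation in 2.8.1 that intensity does not increase. A reader might infer that the planned outcomes cannot distinguish prolongation from a higher second peak. The documents do not support that. What remains is that the average is diluted and the peak does not say when it occurred.

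The plan also has other relevant outputs. Numbers above cut-off are in both analyses, duration above cut-off is in #3, and SAP 6.5 tabulates the time point above cut-off. SAP 6.5.3 Analysis #2 compares adverse events by total dose, with and without the supplement, which bears on the tolerability hypothesis. These count. But the count and duration cover the whole session, all three cut-off measures register only threshold crossings, and in Stage 1 duration is analysed by condition (Analysis #1), not by supplement.

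The post-drug average might mean late-session readings only. The dilution would then largely vanish. The SAP does not settle this.

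Finally, the supplement is not randomised, there are 12 participants, and the number of sessions without a supplement is not stated. A better window does not remove confounding by indication. That stands, and limits what any version of this comparison can claim.

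**Conclusion.** The point holds in a limited form. No outcome in SAP 6.5.1 Analyses #2 or #3 is confined to readings after the supplement. The pre-drug average is uninformative about it. A BP or pulse effect is reduced to about 0.50 to 0.58 of its size if the post-drug average covers all readings after the first dose and readings follow Table 3. For temperature the share kept is 0.60 to 0.75, and for SUDS 0.50 to 0.71. The peak shows 0 to 20% of the effect under the assumed half-size responses fitted to section 4.2, but would reveal a new maximum, which section 4.2 also allows. Selective withholding adds a bias that the earlier readings carry into the outcomes.

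Two stronger readings should be avoided. One is that the effect is simply halved or hidden: the first depends on an undefined average and on the measure, the second on the supplement creating no new maximum. The other is that the fault would persist even if every participant took the supplement. The planned test contrasts given with not given, so there would then be no contrast to dilute.

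This is a low-cost improvement to a safety analysis. It does not bear on the efficacy analyses.

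**What to change.** In SAP 6.5.1 Analyses #2 and #3, where the supplement is the question:

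- Add the mean and maximum of readings after the recorded supplement time, or after the 2.5 h point if none was given. Adjust for the last reading before that point, or express as change from it. Use recorded times, because Protocol 2.8.5.1 leaves exact timing to the therapists. This assumes that dose and reading times were recorded.
- Report the maximum after minus the maximum before, by condition, as a direct description of the expectation in Protocol 2.8.1.
- Drop the pre-drug average as a supplement outcome.
- State which readings form the post-drug average.
- Keep the existing peak and cut-off summaries.
- Label the supplement comparison descriptive, because the supplement is not randomised.

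The cost is SAP wording and a few derived variables per measure, with no new measurements and no change to dosing or monitoring. The price is precision: each window has fewer readings, so its mean is noisier. Temperature and SUDS have only two scheduled readings between the first dose and the supplement, and SUDS may have as few as two after it.
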